8.7. Phase 2/Phase 2 Extension HER2/neu overexpression (Screening)

Confirmation of HER2/neu overexpression is required for inclusion in this study.

A previous pathology result confirming HER2/neu overexpression is acceptable. If analysis of a tumor biopsy is required for confirmation of HER2/neu overexpression, then this may be achieved via analysis of a fresh or archived tissue sample.

HER2/neu analysis will be conducted at each center's local pathology laboratory by immunohistochemistry (IHC) and fluorescent *in situ* hybridization [FISH], brightfield double *in situ* hybridization [BDISH], or chromogenic *in situ* hybridization [CISH] if IHC result is equivocal.

Using the IHC method an unequivocal result of HER2 overexpression is defined as HER2 +++, an equivocal result is defined as HER2 ++, and a negative result is defined as HER2 +. If equivocal result (IHC HER2++) then additional analysis via FISH, BDISH or CISH will be conducted for confirmation of HER2 overexpression. The definition of FISH, BDISH or CISH positivity in gastric or gastro-esophageal junction cancer is a HER2: chromosome 17 ratio of ≥ 2.0 .

8.8. Phase 2/Phase 2 Extension ECOG performance grade (Screening, Baseline, Days 84 then every 84 days and EoT visit)

The ECOG performance grade should be determined using the criteria defined in [Appendix 3: ECOG Performance Status Scale](#).

8.9. Phase 2/Phase 2 Extension Pregnancy Test (at each study visit, excluding post- treatment follow-up visits)

For female patients of childbearing potential, a urine pregnancy test, with sensitivity of at least 25 mIU/mL, will be performed immediately before administration of each vaccine dose. A negative pregnancy test result is required before the patient may receive the investigational product. If urine pregnancy test is positive, then confirmation of pregnancy will be by local laboratory BHCG blood test. If BHCG blood test is negative, then vaccination schedule may resume.

8.10. Phase 2/Phase 2 Extension Intra-tumor analysis (Screening, Day 84 and post- progression)

A screening visit or archival tumor biopsy sample will be obtained for all patients for intra-tumor analysis (unless HER2 status has been confirmed previously and archival tissue is not available). An optional Day 84 and optional post-progression tumor sample will be requested from patients. These samples will be analyzed for intra-tumor T cells and biochemical markers. The screening visit biopsy sample may also be used to determine HER2/neu overexpression.

8.11. Phase 2/Phase 2 Extension Unscheduled Visit

Unscheduled visits may be conducted at any time during Phase 2 by the investigator if clinically indicated for the care of the patient.

Investigational Product: IMU-131
Protocol Identifier: IMU.ACS.001
Protocol Version: Protocol Global Amendment #5, 27 September 2023

An unscheduled visit may include any of the protocol required assessments listed in [Section 8: Phase 2 Assessments](#). The exact assessments conducted at the unscheduled visit will be specified by the investigator and recorded in the CRF. Additional tests and procedures may be performed at the unscheduled visit for the clinical care of the patient after discussion with, and agreement of, the medical monitor.

8.12. Phase 2 Post-treatment Follow Up (FU) Visit (Every 42 days after EoT visit)

After disease progression, anti-cancer therapy and survival information will be collected every 6 weeks until death, withdrawal or end of trial. Anti-cancer therapy and survival information may be collected more frequently than every 6 weeks for quality control and data cleaning purposes. After discontinuation from the study for any reason other than disease progression, radiographic change will be collected every 6 weeks until determination of progressive disease.

All patients will be followed for radiographic change until determination of progressive disease and survival information and anti-cancer treatment until death, unless the patient requests to be withdrawn from radiographic change assessment and survival follow-up contact or the trial ends. Requests for withdrawal must be documented in the source documents and signed by the investigator.

Phase 2 extension patients will no longer complete Post-Treatment Follow Up visits.

9. ADVERSE EVENT REPORTING

9.1. Adverse Events

All observed or volunteered AEs regardless of treatment group or suspected causal relationship to the investigational product(s) will be reported as described in the following sections. All AEs will be collected in response to a general question about the subject's well-being and any possible changes from the baseline or previous visit, but shall not be specifically solicited with respect to particular AEs.

For all AEs, the investigator must pursue and obtain information adequate both to determine the outcome of the AE and to assess whether it meets the criteria for classification as an SAE requiring immediate notification to Imugene Limited or its designated representative. For all AEs, sufficient information should be obtained by the investigator to determine the causality of the AE. The investigator is required to assess causality. AEs will be followed until resolved, stable, or until the subject's last study visit or lost to follow-up. If an AE is not resolved or stabilized at the subject's last visit, it is up to the discretion of the investigator and the Sponsor's medical monitor to determine if further monitoring of the event is warranted.

As part of ongoing safety reviews conducted by the Sponsor, any non-serious adverse event that is determined by the Sponsor to be serious will be reported by the Sponsor as an SAE. To assist in the determination of case seriousness further information may be requested from the investigator to provide clarity and understanding of the event in the context of the clinical trial.

9.2. Reporting Period

For AEs/SAEs, the active reporting period to Imugene Limited or its designated representative begins from the time that the patient provides informed consent, which is obtained prior to the patient's participation in the study, i.e., prior to undergoing any study-related procedure and/or receiving investigational product, through and including 28 calendar days after the last administration of the investigational product, including administration during long term maintenance. After informed consent has been obtained but prior to initiation of study drug(s), only SAEs caused by a protocol-mandated intervention (e.g., invasive procedures such as biopsies, discontinuation of medications) should be reported.

The cause of death must be reported as an SAE if it occurs at any time after the SAE reporting period and is likely to be related to the investigational product.

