- H Cardiac assessment will be based on assessment of medical history, physical examination, 12-lead ECG results and evaluation LVEF by echocardiography or MUGA scan at Screening, Days 84 then every 84 days and at EoT visit.
- I No tumor biopsy is required if a previous pathology result or archival tissue is available confirming HER2/neu expression consistent with Inclusion Criteria #6.
- J Optional Day 84 and post-progression tumor biopsy (which may be provided at any time post progression).
- K Visit only for 'IMU-131 plus chemotherapy' group.
- L Record temperature 30min (+/- 10mins) after each IMU-131 vaccination.
- M Local laboratory testing. Safety lab samples can be drawn up to 72 hours before any on-study clinic visit.
- N A targeted, symptom directed physical examination may be performed at visits occurring after the Baseline Visit.
- O When progressive disease or withdrawal from study has been confirmed, EoT visit will be conducted at least 28 Days (+/- 7) after last dose of study medication. AEs to be checked at least 28 days after last study treatment per [Section 9.2: Reporting Period](#).
- P Phase 2 Extension only: Screening 40 mL cellular immunity blood sample after enrolment eligibility including HER2 over-expression is confirmed.
- Q Phase 2 only: Phase 2 Extension patients will no longer complete Post Treatment Follow Up Visits

Investigational Product: IMU-131
Protocol Identifier: IMU.ACS.001
Protocol Version: Protocol Global Amendment #5, 27 September 2023

R R End of trial is defined as 28 days post the last patient completing the end of treatment visit.

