5.2.1. Formulation and Packaging

The investigational product, IMU-131, will be supplied as P467-CRM197 (aqueous phase vaccine) and Montanide ISA 51 VG (adjuvant) in separate boxes. Each box of P467-CRM197 contains 1 vial of 200 µg aqueous phase vaccine in 1 mL PBS buffer, two vial adapters, two luer-lock syringes, one dosing syringe and needle and one I connector. Each box of Montanide contains a single 3 mL vial of Montanide ISA 51 VG.

Chemotherapy is a standard of care treatment and will be sourced and stored by Pharmacy under usual and standard conditions.

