Patients in the 'IMU-131 plus chemotherapy' group will receive injections of IMU-131 at 50µg in a 0.5mL injection volume on Days 0, 14, 35, 77, 140 and then every 63 days until disease progression.

Phase 2 Extension

IMU-131 administration:

A total of 3 injections of IMU-131-Montanide emulsion (IMU-131 vaccine) at a particular dose will be given to patients in the Phase 2 dose escalation study on Days 0, 14, and 35, and then every 63 days with chemotherapy cycles every 21 days (to a maximum of 6 cycles) starting from Day 0 prior to safety assessment by CRC.

The IMU-131 vaccine will be administered IM into the deltoid region of the upper arm with a 25-38mm (1-1.5 inches), 21-23G needle.

Refer to the study pharmacy manual for detailed IMU-131 vaccine preparation and administration instructions.

Chemotherapy administration in Phase 2 and Phase 2 Extension:

Patients in both the IMU-131 plus chemotherapy group and the chemotherapy alone group will receive chemotherapy starting at the Baseline/Day 0 Visit and then every 21 days for a maximum of 6 cycles as clinically indicated or until disease progression, whichever occurs sooner. One or more chemotherapy treatments may be varied by dose, frequency or discontinued completely as determined by the investigator for the clinical care of the patient.

Chemotherapy will be administered as a concomitant therapy to all patients as a 21-day regimen starting at Day 0 and consisting of: cisplatin by intravenous administration at 80 mg/m² on the first day of each cycle and either 5-FU, 4000 mg/m² CIV (administered as 1000 mg/m²/day as continuous infusion for 96 hours on days 1 to 4 of each cycle) or capecitabine for 14 days at 2000 mg/m²/day, orally (administered as 1000 mg/m² twice daily morning and evening for a total of 2000 mg/m²/day on days 1 to 14 of each cycle), or oxaliplatin, by intravenous administration at 130 mg/m² on Day 1 of each cycle and capecitabine for 14 days at 2000 mg/m²/day, orally (administered as 1000 mg/m² twice daily morning and evening for a total of 2000 mg/m²/day on days 1 to 14 of each cycle).

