10.4.3. Phase 2 Safety Analysis

All safety analyses will be conducted in the safety population.

AEs will be coded according to the Medical Dictionary for Regulatory Activities (MedDRA), version 21.0, or higher. The severity of AEs will be graded according to NCI CTCAE, version 5.0.

Treatment-emergent adverse events (TEAEs) are defined as any AE occurring or worsening on or after the first study drug dose and within 30 days after the last dose date. TEAEs, TEAEs leading to study drug discontinuation, TEAEs leading to dose reduction/interruption, TEAEs related to study drug, SAEs, and TEAEs with an outcome of death will be summarized by system organ class, and preferred term for each treatment group. A summary of TEAEs of NCI CTCAE Grade 3 or higher, as well as the most frequent TEAEs (preferred terms), and TEAEs by relationship to study treatment, will be provided. AE incidence rates will also be summarized adjusting for duration of study treatment.

Values and changes from baseline in clinical laboratory results will be summarized by visit. Clinical laboratory values will be graded according to NCI CTCAE 5.0, for applicable tests. Shifts in toxicity grades from baseline grade will be summarized.

Vital signs, ECG, and concomitant medication data will be summarized. Graphical displays will be provided where useful to assist in the interpretation of results.

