### 9.1. Adverse Events

Adverse events (AE) will be coded using the MedDRA version 21.0 or higher. The severity of AEs will be graded according to National Cancer Institute's Common Toxicity Criteria for Adverse Events version 5.0 (CTCTAE v5.0).

A TEAE is defined as any AE occurring or worsening on or after the first administration of any study drug and within 30 days after the last administration date. Any AE for which the onset date is missing, and the end date is on or after the first dose of any study drug or missing will be counted as TEAE. For the purpose of inclusion in TEAE summaries, incomplete adverse event onset and end dates will be imputed as described in [Appendix 2](#).

A treatment-related TEAE is defined as any TEAE which is reported as "Possible Related", "Probably Related" or "Definitely Related" to any study treatment on the eCRF pages. Any TEAE with a missing relationship or a relationship of "Not Applicable" will be considered as a treatment-related TEAE.

A TEAE leading to treatment discontinuation is defined as any TEAE which is reported with an action of 'Permanently discontinued' taken with any study treatment on the eCRF pages. A TEAE leading to treatment reduction or interruption is defined as any TEAE which is reported with an action of 'Dose decreased' or 'Stopped temporarily' taken with any study treatment on the eCRF pages.

Unless otherwise specified, for the frequency summaries of TEAE, the number and percentage of patients who experienced the specific event, and the number of events will be provided. For the number of patients with the specific event, patients with multiple occurrences of the specific event will be counted only once. For the number event, each occurrence of the specific event will be counted. The SOC will be presented in the descending order of the overall incidence and then alphabetically if two or more SOC have the same incidence; the PT within each SOC will be presented in the descending order of the overall incidence and then alphabetically if two or more PT have the same incidence.

Frequency tables for the following TEAE categories will be provided by SOC and PT for each treatment group and in total. An overview summary table for these TEAE categories will be provided.

- TEAEs
- TEAEs leading to treatment discontinuation
- TEAEs leading to treatment reduction or interruption
- Treatment-related TEAEs
- Serious TEAEs
- Grade 3 or higher TEAEs
- TEAEs leading to death

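### AE reporting, the end-of-treatment AE check and the TEAE window use different anchors and lengths, so they close on different dates for the same patient

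*Protocol*

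**What the plan says.** Three linked rules govern which adverse events are collected and counted after treatment.

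**Reporting period (Protocol 9.2).** AEs and SAEs are reported "through and including 28 calendar days after the last administration of the investigational product, including administration during long term maintenance". Section 5.2.1 identifies that product: "The investigational product, IMU-131, will be supplied as P467-CRM197 (aqueous phase vaccine". Section 5.2.3 places chemotherapy outside it: "Chemotherapy will be administered as a concomitant therapy to all patients as a 21-day regimen". After the period closes, 9.2 asks only for deaths likely to be related to the investigational product.

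**Final AE check (Protocol 6.4.13, Table 3 footnote O, SAP Appendix 1 footnote P).** The "EoT visit will be conducted at least 28 Days (+/- 7) after last dose of study medication". The same provisions have AEs checked at least 28 days after the last study treatment and give 9.2 as the source. AEs are recorded at every study visit except post-treatment follow-up (Protocol 8.3), and Extension patients have no follow-up visits.

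**Counting window.** Protocol 10.4.3 defines a TEAE as "any AE occurring or worsening on or after the first study drug dose and within 30 days after the last dose date", and 10.6 repeats this for the Extension. SAP 9.1 starts the window at the first administration of any study drug and closes it "within 30 days after the last administration date".

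Protocol 9.1 applies AE reporting to both arms: "All observed or volunteered AEs regardless of treatment group or suspected causal relationship to the investigational product(s) will be reported".

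**The concern.** The rule that generates the safety data should reach at least as far as the rule that counts them, and both should work the same way in each arm. Here the first is tied to IMU-131 for 28 days, the second to study treatment for at least 28 days, and the third to an unspecified last dose for 30 days. A control patient never receives the product that 9.2 counts from. In the vaccine arm, doses are up to 63 days apart while chemotherapy runs every 21 days, so a patient can still be on chemotherapy when the 28 days run out.

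The wording of 9.2 does not look like loose shorthand. The section uses the broader plural term study drug(s) for the start of dosing, and Section 9.9 names chemotherapy and IMU-131 separately when it means both. Comparing safety between the arms is a stated Phase 2 secondary objective, so the end of collection should not depend on which of three sentences a site follows.

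**Working it through.** The only stated figure is the 28-day rule itself. The check is date arithmetic.

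**Inputs**
- 9.2 closing day = last IMU-131 day + 28.
- Vaccinations on Days 0, 14, 35, 77, 140, then every 63 days; chemotherapy cycles start on Days 0, 21, 42, 63, 84, 105 (Protocol 5.2.3, Table 3).
- Within a cycle, 5-FU runs on days 1 to 4 and capecitabine on days 1 to 14 (5.2.3). For cycle 6 that means Days 105 to 108 and Days 105 to 118.
- The Day 77 and Day 105 visits each have a window of +/- 7 days (6.4.8, 6.4.10).
- TEAE closing day = last dose + 30.
- Assumption: last dose means the last dose of any study treatment. The TEAE text does not say so. It is inferred from SAP 9.1, which opens the window at any study drug, and SAP 7.3.1, which ends treatment at the later of the last injection and the last chemotherapy.

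**Step 1. Where 9.2 closes in the vaccine arm**

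| Last vaccination | 9.2 closes | Chemotherapy cycles, if continued |
|---|---|---|
| Day 14 | 14 + 28 = 42 | cycle 3 starts that day; cycles 4 to 6 start later |
| Day 35 | 35 + 28 = 63 | cycle 4 starts that day; cycles 5 and 6 start later |
| Day 77 | 77 + 28 = 105 | cycle 6 starts that day |
| Day 140 | 140 + 28 = 168 | all cycles finished |

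Progression at the Day 126 scan gives the Day 77 row. At nominal days the period closes on the day cycle 6 starts. To close before it, the last vaccination must be earlier, chemotherapy must be delayed, or the visits must drift. With vaccination on Day 77 - 7 = 70 and cycle 6 on Day 105 + 7 = 112, it closes on Day 70 + 28 = 98, which is 112 - 98 = 14 days before cycle 6.

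**Step 2. 9.2 against the TEAE window, Day 77 last and cycle 6 on Day 105**

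| Last dose taken as | TEAE window closes | Shortfall from Day 105 |
|---|---|---|
| start of cycle 6, Day 105 | 135 | 30 days |
| last 5-FU day, Day 108 | 138 | 33 days |
| last capecitabine day, Day 118 | 148 | 43 days |

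If the Day 140 vaccination is the last dose of any treatment, the TEAE window closes on Day 170 and 9.2 on Day 168, a shortfall of 2 days.

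**Step 3. EoT provisions against the TEAE window, either arm**

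The AE check has a floor of 28 days after the last study treatment, so the guaranteed shortfall is at most 30 - 28 = 2 days. With last capecitabine on Day 118, the floor is Day 146 and the window closes on Day 148. A check made 30 to 35 days after the last dose leaves no shortfall. The visit tolerance would allow EoT at 28 - 7 = 21 days (Day 139 here), before the AE check may take place under the same footnote.

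**Step 4. Chemotherapy-alone arm**

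There is no IMU-131 date, so 9.2 yields no closing day. For last capecitabine on Day 118, the EoT provisions give Day 146 at the earliest and the TEAE definition gives Day 148.

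**The case against.** The strongest reply is that 9.2 is not applied in isolation. Footnote O, 6.4.13 and SAP footnote P cite it and express it as last study treatment, so the protocol's own cross-reference gives both arms a working end point. AE recording is mandatory at Days 105 and 126 and at EoT. Section 9.12.2 sends AEs and SAEs after consent to the CRF with no product-based stop. A vaccination is known to be the last only in hindsight: until the Day 126 scan, the Day 140 dose is still scheduled, so a site has no basis to stop on Day 105. All of this stands, and it means that actual data loss may be small. It does not make the three rules agree.

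Four stronger readings are tempting and are not supported.
- **Control-arm collection never ends, or is never required.** This holds only for 9.2 read alone.
- **An EoT visit at 21 days leaves 30 - 21 = 9 TEAE days uncollected.** The AE check has its own 28-day floor with no minus tolerance. What remains is an internal contradiction in the timing.
- **35 of every 63 days between boosters (63 - 28 = 35, or 56%) fall outside reporting.** This too treats each dose as the last before anyone could know it.
- **The safety comparison is biased towards the vaccine, or events are withheld from the IDMC.** Vaccine-arm patients have extra AE-recording visits on Days 14, 35, 77 and 140, which could push ascertainment the other way. The IDMC's review procedures are in a charter that is not among these documents.

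**Conclusion.** The inconsistency is real and should be corrected. Three rules that depend on each other give different closing dates, and 9.2 taken alone gives none for control patients.

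The size depends on the sentence followed. Under the EoT provisions, guaranteed collection is up to 2 days short of the TEAE window in either arm. Under a literal reading of 9.2, the shortfall in the Day 77 example is about 30 to 43 days. The upper end assumes capecitabine through Day 118, and the whole range assumes that last dose means any study treatment. A literal reading could also make ascertainment differ by arm, but the documents do not allow the direction or size of any bias to be determined. In the single-arm Extension there is no between-arm issue, only the mismatch of anchors and lengths.

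**What to change.** - **Protocol 9.2:** end AE and SAE reporting a fixed number of days after the last dose of any study treatment (IMU-131 or protocol chemotherapy), in both Phase 2 arms and in the Extension.
- **One length:** use the same number, for example 30 days, for the reporting period, the final AE check and the TEAE window. Shortening the TEAE window to 28 days would also remove the 2-day mismatch, but only a common anchor removes the larger one.
- **TEAE definition (Protocol 10.4.3 and 10.6, SAP 9.1):** state that the last dose is the last dose of any study treatment.
- **Protocol 6.4.13, Table 3 footnote O and SAP Appendix 1 footnote P:** reconcile the minimum of 28 days with the +/- 7 tolerance, so that the final AE check does not fall before the window ends. Protocol 8.1 already allows AEs to be documented by telemedicine, so a remote contact would do.

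The cost is wording in both documents and a last AE check a few days later for some patients. No clinic visit is added.

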9.3. Definition of an Adverse Event

An AE is any untoward medical occurrence in a clinical investigation patient administered a product or medical device; the event need not necessarily have a causal relationship with the treatment or usage. Examples of AEs include but are not limited to:

- Abnormal test findings;
- Clinically significant symptoms and signs;
- Changes in physical examination findings;
- Hypersensitivity;
- Drug abuse;
- Drug dependency.

Additionally, they may include the signs or symptoms resulting from:

- Drug overdose;
- Drug withdrawal;
- Drug misuse;
- Drug interactions;
- Extravasation;
- Exposure during pregnancy;
- Exposure via breastfeeding;
- Medication error;
- Worsening of signs and symptoms of the malignancy under study should be reported as AEs in the appropriate section of the CRF. Disease progression assessed by measurement of malignant lesions on radiographs or other methods should not be reported as AEs.

